9.13.2 Demographics and Disease Characteristics

All baseline and disease characteristics will be summarized for the CP stratified by the CP analysis groups (i.e. based on genotype 1 subtype, fibrosis status, treatment experienced or naïve), which are relevant for scheduled treatment combination (ABBVIE REGIMEN) and duration (12 weeks). In addition, baseline summaries will be repeated for the SP and the TP without stratification into subgroups. Summary statistics (n, mean, median, standard deviation [SD], and range) will be generated for continuous variables (e.g. age and body mass index [BMI]). The number and percentage of patients will be presented for categorical variables (e.g. gender and race). Further details of analysis populations and the CP analysis groups will be specified in the SAP, taking into account the ABBVIE REGIMEN recommended in the current local label for various patient groups.

9.13.3 Effectiveness Analysis

The primary effectiveness analysis on clinical outcomes will be performed on all patients in the CP stratified by the CP analysis groups. Due to the non-interventional nature of this study several different methods for determination of the HCV RNA value can be applied. For the purpose of the statistical analysis, a HCV RNA measurement is considered ≤ 50 IU/mL,

- if a PCR test was used
- and the test result is undetectable and the LLoD of the test is ≤ 50 IU/mL or the test result is unquantifiable and the LLoQ is ≤ 50 IU/mL

9.13.4 Primary Effectiveness Endpoint

The percentage of patients achieving SVR12 (single last HCV RNA <50 IU/mL 12 weeks [i.e. at least 84 days] after the last actual dose of the ABBVIE REGIMEN) is the primary effectiveness endpoint.

9.13.5 Secondary Effectiveness Endpoints

The secondary effectiveness endpoints are:

- The percentage of patients with virological response (HCV RNA <50 IU/mL) at EoT
- The percentage of patients with relapse (defined as HCV RNA <50 IU/mL at EoT followed by HCV RNA ≥ 50 IU/mL)
- The percentage of patients with relapse (defined as at least one documented HCV RNA <50 IU/mL followed by HCV RNA ≥ 50 IU/mL during treatment).

- The number and percentage of patients meeting each and any of the following SVR12 non-response categories:
 - Relapse (defined as HCV RNA <50 IU/mL at EoT or at the last on-treatment HCV RNA measurement followed by HCV RNA ≥ 50 IU/mL post-treatment)
 - Missing SVR12 data and/or none of the above criteria

9.13.6 Statistical Methods for Analysis of Effectiveness Variables

The simple percentage of patients achieving SVR12 will be calculated and an exact two-sided 95% confidence interval (CI) of the percentage will be computed based on the Clopper-Pearson method.

Corresponding methods will be used for other response rates (EoT response rate, relapse rate). The relapse rates will be estimated in patients of the CP analysis groups with EoT response and sufficient HCV RNA measurements post-treatment.

These analyses will be of exploratory nature, data driven, and will be repeatedly performed for various CP Analysis Groups, since not each covariate might be predictive in each patient group. Furthermore, the fact that treatment regimens will differ in the various patient groups has to be taken into account, when selecting the patient groups for each MLR analysis. Backward selection procedures will be applied to generate the final MLR models which consider only covariates in the selection procedure with a p-value <0.25 in the corresponding univariate logistic regression analysis. A p-value <0.05 will be used for the covariates to stay in the model in a backward elimination step. Logistic regression methods will also be used to investigate the impact of treatment adherence on SVR12.

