9.11 Study Size

60 patients will be included in this descriptive study without any priory sample size calculation. Convenient sampling methods will be used for patients who attended routine outpatient visits, fulfilled the inclusion/exclusion criteria and had signed a patient authorization form to use and disclose personal health information.

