No data will be imputed for any effectiveness or safety analyses except for the analyses of the HCV RNA endpoints. When there is no HCV RNA value in a visit time window post-baseline, but prior to EoT, the closest values before and after the window, regardless of the value chosen for the subsequent and preceding window, will be used for the flanking imputation described below. If a patient has a missing HCV RNA value at a post-Visit 1

visit prior to EoT but has undetectable HCV RNA (with LLoD \leq 50 IU/mL) or unquantifiable, but detectable HCV RNA levels (with LLoQ \leq 50 IU/mL) at both the preceding and succeeding measurements, the HCV RNA level will be considered undetectable or unquantifiable, respectively, at this visit for this patient. In addition, if a patient has an unquantifiable HCV RNA level at the preceding measurement and an undetectable HCV RNA level at the succeeding measurement, or vice versa, the HCV RNA level will be imputed as unquantifiable at this visit for this patient. For virological response at EoT a corresponding backward imputation approach will be applied. This means if HCV RNA is missing at EoT, then unquantifiable or undetectable will be assumed for EoT, if the succeeding HCV RNA value is undetectable or unquantifiable. For SVR12 the single last available HCV RNA measurement \geq 84 days post-treatment will be used. Subsequent to this flanking and backward imputation, if the HCV RNA value remains missing at a specific time point, then the patients will be considered as virological failure at this time point (i.e. not undetectable or unquantifiable).

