 - relapse after EoT (HCV RNA value <50 IU/mL or undetectable/negative at EoT or at the last on-treatment HCV RNA measurement followed by HCV RNA \geq 50 IU/mL or positive post-treatment);
 - failure to suppress (each measured on-treatment HCV RNA value \geq 50 IU/mL or positive);
 - premature study drug discontinuation with no on-treatment virologic failure;
 - missing SVR12 data and/or none of the above criteria.

Figure 9.1 illustrates the patient's distribution by SVR12 response/non-response categories.

P16-253 (CITRIN) _ STATISTICAL ANALYSIS PLAN _ FINAL 2.0 _ 16 Mar 2018

[figure not shown]

Figure 9.1 – Patient's distribution by SVR12 response/non-response categories. Frequencies and percentages with 95% confidence intervals will be calculated for each effectiveness outcomes and will be presented according the section 7.1. Also frequency tables will be repeated for patients in subgroup without missing SVR12 data category.

Effectiveness endpoints (SVR12 achieving, virological response at EoT and relapse after EoT) will be analyzed using univariate logistic regression, if applicable. These analyses will be of exploratory nature, data driven, and will be repeatedly performed for various CP analysis groups, since not each covariate might be predictive in each patient group.

The following parameters can be included in the univariate models as explanatory variables (fixed effect or covariate):

- treatment experience (with/without prior treatment for CHC);
- Child Pugh score;
- result of FibroTest;
- history of liver decompensation;
- age;
- gender;
- race;
- BMI;
- laboratory hematology¹:
 - hemoglobin;
 - platelets;
 - prothrombin time;
 - laboratory clinical chemistry:
 - ALT;

¹ Note that all Hematology variables and all Clinical Chemistry should be in the same units. If it is impossible to bring units to the same the smallest units groups will be accepted as missing. If it is impossible to identify the smallest units groups the corresponding covariate will be deleted from the analysis.

P16-253 (CITRIN) _ STATISTICAL ANALYSIS PLAN _ FINAL 2.0 _ 16 Mar 2018

- AST;
- Gamma-GT;
- total bilirubin;
- albumin;
- creatinine clearance;
- alpha-1-fetoprotein.

Additionally, after univariate model analyses all effectiveness endpoints can be analyzed using MLR (if applicable) which consider only covariates in the selection procedure with a p-value <0.25 in the corresponding univariate logistic regression analysis¹.

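### The TP and CP regressions for SVR12 score untested patients as virological failures, and neither document says which population's models are to be interpreted

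*Protocol*

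**What the plan says.** Protocol 9.13.1 sets the missing-data rule. After the flanking and backward imputation, "if the HCV RNA value remains missing at a specific time point, then the patients will be considered as virological failure". Protocol 9.13.3 names the lead population: "The primary effectiveness analysis on clinical outcomes will be performed on all patients in the CP stratified by the CP analysis groups".

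Protocol 9.13.6 describes exploratory logistic models that "will be repeatedly performed for various CP Analysis Groups, since not each covariate might be predictive in each patient group". Covariates are screened at p<0.25 in univariate models, and then "A p-value <0.05 will be used for the covariates to stay in the model in a backward elimination step". It adds: "Logistic regression methods will also be used to investigate the impact of treatment adherence on SVR12". It gives no separate outcome or population for any of these models.

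SAP section 9 states: "Effectiveness endpoints (SVR12 achieving, virological response at EoT and relapse after EoT) will be analyzed using univariate logistic regression, if applicable". It requires all effectiveness analyses in the TP, CP and CPSFU, and section 16.1 lists SVR12 regression tables in three corresponding blocks. Missing SVR12 data is one of the non-response categories, and the percentage shells use the whole population as denominator. The repeat without missing SVR12 data covers the frequency tables only.

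The CPSFU (Protocol 9.13.1, SAP section 6) leaves out patients who were responding at their last test and whose SVR12 test is missing for reasons unrelated to safety or effectiveness. Its third criterion keeps patients last seen below 50 IU/mL who have no SVR12 test for safety reasons or because the efficacy information is incomplete.

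**The concern.** Counting a missing test as failure is a sound conservative rule for a response percentage, because it can only lower the estimate. It has no such property for an odds ratio. If a covariate is related to coming back for the test, the rule gives it an apparent relation to cure. If a covariate truly affects virological failure, the untested patients dilute it.

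Two features make this more than theoretical here. HCV RNA testing is left to the physician's discretion (Protocol 9.13.1), so some tests will probably be missing. The regimen is also expected to cure nearly everyone, so true failures will be few and a small number of untested patients can dominate the outcome. The screening and backward-elimination rules could then carry a predictor of follow-up into a final model presented as a model of SVR12. Protocol 9.15 warns that missing tests lower the SVR rate but says nothing about the regressions.

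**Working it through.** **The plan's own figure.** Both the Protocol abstract and section 7.0 cite SVR12 in 60 of 60 patients, 95% CI 94.0–100%. The exact (Clopper-Pearson) lower limit is 0.025^(1/60) = 0.9404, so 94.0% is reproduced. The matching range for true failure is 0 to 6%.

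**Inputs.** N = 60 (Protocol 9.11: "60 patients will be included in this descriptive study without any priory sample size calculation"). True failure among tested patients, f: 1%, 3% and 6%, within the range above. Probability of no SVR12 test, m: not given in either document, so a range of 2% to 20% is assumed.

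**Step 1: share of modelled failures that are missing tests.** Untested patients contribute m and true failures contribute (1 − m)f, so the share is m / (m + (1 − m)f). For example, at m = 10% and f = 3%: 0.10 / (0.10 + 0.90 × 0.03) = 0.10 / 0.127 = 79%.

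| f | m = 2% | m = 5% | m = 10% | m = 20% |
|---|---|---|---|---|
| 1% | 67% | 84% | 92% | 96% |
| 3% | 40% | 64% | 79% | 89% |
| 6% | 25% | 47% | 65% | 81% |

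**Step 2: break-even.** Untested patients outnumber true failures when m > (1 − m)f, that is, m > f/(1 + f). This is 1.0%, 2.9% and 5.7% at f = 1%, 3% and 6%, or about 0.6, 1.7 and 3.4 of 60 patients.

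**Step 3: effect on an odds ratio.** Take a binary covariate splitting patients 50/50. In the first case it triples the odds of a missing test and has no effect on failure. In the second it triples the odds of failure and has no effect on testing. The combined outcome has probability m + (1 − m)f in each half.

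| f | m | OR shown when only missingness has OR 3 | OR shown when only failure has OR 3 |
|---|---|---|---|
| 1% | 10% | 2.70 | 1.10 |
| 3% | 10% | 2.31 | 1.27 |
| 6% | 10% | 1.97 | 1.49 |
| 3% | 2% | 1.51 | 1.88 |
| 6% | 2% | 1.29 | 2.24 |

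The second row, first case, in full: missing probabilities of 5.4% and 14.6% average 10% with odds ratio 3. The combined outcome is 0.0539 + 0.9461 × 0.03 = 0.0823 and 0.1461 + 0.8539 × 0.03 = 0.1717. The odds ratio is 0.2073 / 0.0897 = 2.31, where the true value for virological failure is 1. In the last two rows the order reverses and the real predictor shows more strongly than the artefact.

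**Step 4: what a known-outcome model has to work with.** At N = 60, m = 10% and f = 3% there are 6 untested patients and 54 × 0.03 = 1.6, say 2, true failures. With missing = failure, SVR12 is 52/60 = 86.7% (95% CI 75.4–94.1) and the model has 8 events. Among tested patients SVR12 is 52/54 = 96.3% (87.3–99.5) and the model has 2. Over f = 0–6%, 60 patients yield 0 to 3.6 true failures even if all are tested.

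**The case against.** The strongest reply is that the SAP already contains the remedy. The CPSFU regressions exclude responders lost for unrelated reasons, which is the main mechanism at issue, and SAP section 18 labels the CPSFU percentage tables as the main analysis. This is largely right, but that label is on the percentage tables and not on the regressions, while the Protocol makes the CP primary and places the regressions in CP groups. The population tags do not settle it: section 16.1 marks the regression tables in the CP block as TP, and section 18 says the CPSFU-block regressions are for the core population. Within the CPSFU, a criterion-3 patient last seen below 50 IU/mL with no SVR12 test is still scored as a failure.

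A reader might infer that these models mainly identify who did not return. The documents do not support that as a fact, because it depends on a missing rate they do not state, and at 2% missing with 3–6% true failure it is false. The SAP's CP also excludes patients whose treatment ended by study day 55, so some early discontinuers are not in the CP models.

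A reader might also infer that the adherence model is close to circular. The documents say nothing on how adherence relates to returning for a test. Adherence is also absent from the SAP's covariate list and regression tables, appearing only as an exposure summary (SAP 10.1).

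It is fair to add that the analyses are exploratory and qualified by the words *if applicable*, that missing SVR12 has its own row in the frequency tables, and that the primary percentage is unaffected. The SAP does not separately say how the models code an untested patient. The Protocol's rule is the only one available, and the SAP's non-response categories follow it.

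The last objection stands in full: a known-outcome model will usually have too few events. That is a reason not to fit it, and not a reason to supply events from untested patients. Keeping early documented failures while dropping untested responders also leaves some selection by follow-up, which should be stated as a limitation.

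**Conclusion.** The point holds in a conditional form. In the TP and CP the SVR12 regressions model a mixture of virological failure and absence of a test. With true failure at 0–6%, untested patients form the larger part once about 0.6 to 3.4 of 60 lack a test (f from 1% to 6%). At 10% missing and 3% failure, a covariate with odds ratio 3 for missingness alone shows 2.31, and a genuine predictor with odds ratio 3 shows 1.27. These sizes rest on an assumed missing rate, on the cited trial's failure range carrying over to routine practice, and on 60 analysed patients.

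The CPSFU regressions remove most of the problem but are not designated for interpretation and retain untested criterion-3 patients. The point is confined to the SVR12 models. It does not touch the SVR12 percentage, for which missing = failure remains appropriate.

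**What to change.** In Protocol 9.13.6 and SAP section 9:

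- Make patients with a known virological outcome the population for interpreting SVR12 regressions: an HCV RNA result in the SVR12 window, or a documented virological failure. In effect this is the CPSFU without untested criterion-3 patients who have no documented failure.
- Drop the TP and CP SVR12 regression tables, or retitle their outcome *SVR12 not achieved or not assessed*. Correct the population tags on the remaining regression tables.
- Keep missing = failure for the SVR12 percentage.
- State in advance that with only a handful of known failures the multiple model is not fitted and the failures are described individually.
- Apply the same rule to the adherence regression. The Protocol commits to it and the SAP omits it, although SAP section 15 claims full consistency, so the two need reconciling.

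The cost is some wording and fewer tables. The real downside is fewer events: often no model will be fitted, and the report will describe a few individual failures instead.

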9.13.7 Clinical Laboratory Data

All reported clinical laboratory test results will be assigned to one of the time points using the time windows specified in the table below.

Table 1 - Analysis Time Windows

Time point	Time Window
Visit 1	Last value prior to start of study treatment (i.e. ≤study day 1)
Actual EoT	Study day of last dose (28 days prior to EoT - 14 days post EoT)
12 weeks (day 85 post EoT)	57 – 112 post EoT

Mean changes from baseline to each post-baseline visit will be summarized descriptively.

Laboratory data values collected during the treatment period will be categorized as low, normal, or high based on reference ranges used in this study. The number and percent of patients who experience post-baseline shifts during treatment in clinical laboratory values from low/normal to high and high/normal to low based on the reference range will be summarized.

Additional details of the analyses of clinical laboratory data will be specified in the SAP.

9.13.8 Tolerability Analysis

All tolerability variables will be summarized using descriptive statistical methods for the SP stratified by type of combination treatment and scheduled treatment duration.

All SAEs, non-serious AEs and pregnancy occurrences are to be reported for patients included in the study. AEs will be coded using MedDRA. The number and percentage of patients with treatment-emergent AEs (i.e. any reported event that begins or worsens in severity after initiation of study drug through 30 days post-study drug dosing) will be

tabulated by primary MedDRA SOC and PT. Corresponding summary tables will be provided for all serious treatment-emergent AEs. The tabulation of the number of patients with treatment-emergent AEs by severity and relationship to study drug will also be provided. Patients reporting more than one AE for a given MedDRA PT will be counted only once for that term using the most severe incident for the severity summary table and the most related for the relationship summary table. Patients reporting more than one type of event within a SOC will be counted only once for that SOC.

Additional details of the analysis of AEs will be specified in the SAP.

9.14 Quality Control

The sites will be instructed in the protocol, the functionality and handling of the eCRF, and the requirement to maintain source documents for each patient in the study.

A comprehensive data validation program utilizing front-end checks in the eCRF will validate the data. Automated checks for data consistency will be implemented, discrepancies need to be solved by the researcher in the eCRF before the module can be completed. Follow-up on eCRF data for medical plausibility will be done by AbbVie personnel (or their representatives). The principal investigator of each site will finally review the eCRFs for completeness and accuracy of available data and provide his or her electronic signature and date to eCRFs as evidence thereof.

Continuous monitoring of the study and frequent site telephone contacts will be done by AbbVie or a CRO working on behalf of AbbVie.

9.15 Limitations of the Research Methods

The limitations of observational studies, such as uncontrolled confounding by lack of randomization, and difficulties to clearly interpret treatment effects in the context of missing data are well known. Their validity can be increased by accurate outcome

measurements, documentation of the most common confounders, sufficient length of follow-up and by activities to obtain complete recording of available data as well as by searches for missing key data.

The most important outcome measure in this study is HCV RNA. Missing or unrecorded follow-up HCV RNA data can in particular lead to an underestimation of the real SVR rate as compared to the SVR rate of interventional trials. Highly sensitive and quantitative diagnostic tests are required to measure HCV RNA levels in blood. In an observational study each center will be using its own test – either commercially available or so-called “home-brew” tests – which might change from one visit to the next within a patient data set. The challenge is to accurately and consistently document test properties such as the LLoD and the LLoQ to put the results into perspective of prior outcomes from randomized controlled trials with (usually) central laboratory assessments for all trial participants.

9.16 Other Aspects

Not applicable.

10.0 Protection of Human Subjects

This observational study will be run in compliance with local laws and regulations. Notification/submission to the responsible regulatory authorities, Ethics Committee (EC) and/or Competent Authorities (CAs) will be done as required by local laws and regulations.

The investigator is responsible to ensure that written informed consent will be obtained prior to patient inclusion

To maintain patient confidentiality, no demographic data that can identify the patient will be collected (e.g. initials, date of birth) - only the patient age will be collected. In order to

protect patient identity, a unique number will be assigned to each patient and related study recording.

11.0 Management and Reporting of Complaints

A Complaint is any written, electronic, or oral communication that alleges deficiencies related to the physical characteristics, identity, quality, purity, potency, durability, reliability, safety, effectiveness, or performance of a product/device after it is released for distribution.

Complaints associated with any component of this investigational product must be reported to the Sponsor (Section 11.2.2). For adverse events, please refer to Sections 11.1.1 through 11.1.6. For product complaints, please refer to Section 11.2.

11.1 Medical Complaints

11.1.1 Adverse Event Definition and Serious Adverse Event Categories

An adverse event (AE) is defined as any untoward medical occurrence in a patient, which does not necessarily have a causal relationship with their treatment. An adverse event can therefore be any unfavorable and unintended sign (including an abnormal laboratory finding), symptom, or disease temporally associated with the use of a medicinal product, whether or not the event is considered causally related to the use of the product.

Such an event can result from use of the drug as stipulated in the labeling, as well as from accidental or intentional overdose, drug abuse, or drug withdrawal. Any worsening of a pre-existing condition or illness is considered an adverse event.

If an adverse event meets any of the following criteria, it is considered a serious adverse event (SAE):

Death of Patient:

An event that results in the death of a patient.

Life-Threatening:	An event that, in the opinion of the investigator, would have resulted in immediate fatality if medical intervention had not been taken. This does not include an event that would have been fatal if it had occurred in a more severe form.
Hospitalization:	An event that results in an admission to the hospital for any length of time. This does not include an emergency room visit or admission to an outpatient facility.
Prolongation of Hospitalization:	An event that occurs while the study patient is hospitalized and prolongs the patient's hospital stay.
Congenital Anomaly:	An anomaly detected at or after birth, or any anomaly that results in fetal loss.
Persistent or Significant Disability/Incapacity:	An event that results in a condition that substantially interferes with the activities of daily living of a study patient. Disability is not intended to include experiences of relatively minor medical significance such as headache, nausea, vomiting, diarrhea, influenza, and accidental trauma (e.g., sprained ankle).
Important Medical Event Requiring Medical or Surgical Intervention to Prevent Serious Outcome:	An important medical event that may not be immediately life-threatening or result in death or hospitalization, but based on medical judgment may jeopardize the patient and may require medical or surgical intervention to prevent any of the outcomes listed above (i.e., death of patient, life threatening, hospitalization, prolongation of hospitalization, congenital anomaly, or persistent or significant disability/incapacity). Additionally, any elective or spontaneous abortion or stillbirth is considered an important medical event. Examples of such events include allergic bronchospasm requiring intensive treatment in an emergency room or at home, blood dyscrasias or convulsions that do not result in inpatient hospitalization, or the development of drug dependency or drug abuse.

